### NH level:

- Occupied bed days (in the past 12 months)
- Sex ratio of residents
- Mean age of residents
- Rate of all deceased residents (in the past 12 months)
- Rate of full nurse equivalents per 100 residents
- Rate of palliative care qualified nurses per 100 residents
- Rate of general practitioners per 100 residents

SAP **V01-00** 

- Defined private co-payment for residents (relative deviation from the regional mean)
- Total sick leave days per nursing staff (i.e. number of registered/assistant/hired nurses) (in the past 12 months)

### Residents level:

- Age
- Sex
- Marital status
- Care level
- Professional degree

### 5.3 Missing data

The number of available observations and the number of missing observations of each variable will be presented for the intervention and control group separately, as well as for the total sample. All data will be analysed in an ITT approach.

The main analysis strategy is using all available data of all randomized NHs (full analysis set, FAS). For the primary endpoint (and all secondary endpoints related to DC1) no missing data is expected due to the nature of aggregated data collection.

For the unlikely situation of a substantial rate of missing values (>5%) in the primary outcome, a multiple imputation using chained equations will be applied in the ITT population for a sensitivity analysis. We will follow the recommendations of White, Royston and Wood (2011) in order to set up a proper imputation model assuming missing data to be missing at random (MAR). The imputation model includes simultaneously all above described variables (primary and secondary endpoints) of the DC1 at all measured time points.

The number of imputations (M) will be defined by the percentage of missing values in at least one of those defined variables at all time points. If the assumption of M=100\*FMI (Largest Fraction of Missing Information) is fulfilled, at least 20 imputations will be performed.

## 5.4 Additional analyses

### 5.4.1 Subgroup analyses

To assess the effect of the structural ACP program within specific types of NHs or groups of residents, subgroups according to the following characteristics will be analysed regarding the primary endpoint and key secondary endpoints:

### On NH level:

- Size of NHs (small (< 100 residents) vs. large ( $\geq$  100 residents))
- Study centre (Göttingen, München, Düsseldorf, Halle)

- Ownership (non for-profit vs. municipal)
- Palliative care structure (at least two palliative care nurses (40h or 160h) and palliative care concept vs. none)
- Staffing (care hours per resident > median vs.  $\le$  median)
- Death rate per 100 residents (> median vs. ≤ median)

### On resident level:

- Sex (male vs. female)
- Age (very old aged (> 90 years) vs. old ( $\leq$  90 years))
- Resident capable of decision making (as expressed in who signed his or her consent, the resident or the proxy)
- Years since moving in (> 3.5 vs. < 3.5 Jahre)
- Care level (1,2,3 vs. 4,5)
- Level of education (no degree, vocational or school training or apprenticeship vs. training at a master craftsman/technical school, vocational or technical academy, technical college degree/university degree)

For each of the subgroups the above defined models for the primary endpoint and the key secondary endpoints are supplemented by the subgroup variable and its interaction term with the treatment group. In forest-plots (for each variable) marginal effect measures of the treatment effect and corresponding 95% CIs will be presented for the subgroups and the interaction p-value will be given.

### 5.4.2 Covid-19-Analysis

To assess the effect of the Covid-19 pandemic on the primary outcome, the following analysis is planned:

A mixed Poisson regression model is calculated taking into account group (intervention vs. control), time (t0, t1, t2) as well as the interaction between group and time as fixed effect, realized follow-up time as offset, the respective baseline hospitalization rate as covariate, and region of NHs and the respective NH as random intercept. The aim is to evaluate the effect of Covid-19 as external confounder on the primary outcome over time.

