### 1.2 Objectives

The goal of the multicenter BEVOR study is to evaluate the effectiveness of a structured advance care planning (ACP) program in NH residents regarding the reduction of unwanted medical interventions, notably hospital admissions, as compared to a control group. Conversely, the rate of residents whose treatment preferences are known and honored should be increased.

In the following, the time point of baseline measurement is defined as t0, of the end of the run-in phase of the intervention as t1, and of succeeding 12-months follow-up as t2. For more details, see section 2.7.

Researchers will take two independent approaches for data collection:

Firstly, participating NHs will provide anonymous pooled data on all their residents which include long-term as well as respite care residents of a defined time period (data collection 1 = DC1), including the hospitalization rate (primary outcome).

If not stated otherwise, data of both groups are used, long-term and respite care residents.

Secondly, a cohort of all long-term residents who have given informed consent (or for whom their health care proxy has given informed consent), their health care proxies and/or relatives, and the

respective nursing staff will be repeatedly surveyed until t2 (or until residents die earlier) (data collection 2 = DC2).

The following primary hypothesis will be tested:

**Primary hypothesis:** Compared to the control group, the structured ACP program reduces the 12-month hospitalization rate of residents of NHs at t2.

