## 2.7 Timing of outcome assessments

The timeline of the BEVOR study is as follows (see Fig. 2 of the study protocol): at the start of the study, data collection is initiated, which corresponds with the baseline measurement (t0). At the end of the run-in phase of the intervention, the 12-month observation phase begins (t1). The end of the observation phase corresponds with the measurement at 12-months follow-up (t2). The run-in phase of the intervention describes the time in which the intervention is established and reaches the residents, the NHs and the regions. It lasts from the time of randomization until t1. The intervention itself continues during the observation period.

The 12 months observation period's data will be collected in one follow up collection (DC1) or, respectively, for DC2 continuously over the entire period, including

- interviews with relatives and nursing home staff of deceased residents,
- four three-monthly sessions to identify all potentially life-threatening events and related treatment decisions for the respective preceding 3 months (3CP data collection including interviews), as appropriate.

The start of the observation phase (t1) is fixed for all study centres at 01.09.2021.

**NH level (DC1):** All outcomes on NH level will be measured at t0, t1 and t2 for the preceding 12 months.

**Resident's level (DC2):** Data collection 2 is performed with residents, their surrogates and/or relatives, and the respective nursing staff and contains three different sections with different time points:

- 1. Framework survey including quality of care survey is conducted at t0 and t2 for the 12 months observation period.
- 2. Care consistency with care preferences (3CP) is assessed at t0 for the preceding 3 months and at t2. Data collection at t2 will be splitted into 4 phases of the 12-months observation period (each covering the preceding 3 months), beginning 3 months after t1, to collect data over the twelve months of observation as accurately as possible. It is ensured that there is no overlap in the survey periods.
- 3. The survey of relatives and staff regarding deceased residents is conducted at t0 and continuously over the 12 months before t2.

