### 5.1.2 Primary Outcome

The primary analysis is performed in the ITT population at NH level. For rate comparison a Poisson regression model is calculated taking into account group (intervention vs control) as independent variable, realized follow-up time as offset, region of NHs and the respective baseline hospitalization rate as covariates. The treatment effect is presented as incidence rate ratio (IRR) with corresponding 95%-Confidence interval (CI) and p-value. Marginal estimators (numbers per 100 residents per past 12 -months observation period (from t1 to t2)) with corresponding 95%-CI are given per treatment group.

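### The Covid-19 model (SAP 5.4.2) uses the t0 hospitalization rate as both response and covariate, so its group-by-time term is not baseline-adjusted; separately, it has no Covid-19 variable and cannot meet its stated aim

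*SAP*

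**What the plan says.** Section 1.2 fixes the meaning of baseline: "the time point of baseline measurement is defined as t0". Section 2.7 says of the home-level data: "All outcomes on NH level will be measured at t0, t1 and t2 for the preceding 12 months". Each home therefore supplies three hospitalization counts.

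Section 5.4.2 models all three. Its fixed effects are group, "time (t0, t1, t2) as well as the interaction between group and time as fixed effect". The same sentence then adds "realized follow-up time as offset, the respective baseline hospitalization rate as covariate", with random intercepts for region and home. No product of the baseline rate with time is listed, and the arms are not constrained to be equal at t0. The section ends: "The aim is to evaluate the effect of Covid-19 as external confounder on the primary outcome over time". No infection, outbreak, restriction or pandemic-phase variable is named.

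The primary model in section 5.1.2 has similar covariate wording, "realized follow-up time as offset, region of NHs and the respective baseline hospitalization rate as covariates", but its outcome is the t1 to t2 period only. There the baseline rate is a predictor and nothing else.

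**The concern.** Two separate defects sit in one paragraph.

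The first is the double use of t0. In the t0 rows the model predicts a count from a covariate computed from that same count. A reader who sees the baseline rate listed will assume that the group-by-time result is baseline-adjusted, as the primary result is. It is not. If the two results differ, part of the difference may be chance imbalance at t0, and in a section on Covid-19 it could be misread as a pandemic effect.

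The second is the aim. The model contains only group, time and their product, plus baseline, region and home. It has nothing by which to attribute a change in the rate to Covid-19.

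Section 5.4.3 allows the same kind of Covid-19 analysis for all secondary endpoints, outside the study report, so the specification could be repeated there.

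**Working it through.** Section 5.4.2 states no figure to reproduce. The check is algebra, then a closed-form calculation, then a simulation.

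**1. The covariate cancels from the interaction.** For home i at time t:

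log μ(i,t) = log offset + a + g·G(i) + τ(t) + d(t)·G(i) + b·baseline(i) + u(i), with the region effect omitted.

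The terms a, g·G(i), b·baseline(i) and u(i) do not depend on t. Given a home's total count over the three periods they drop out. If the offset is constant within a home, the estimate of d(t2) equals the raw log ratio of rate ratios: t2 against t0, intervention against control.

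Simulated Poisson data (44 homes, 40 data sets per setting) confirm this. With constant offsets the interaction was the same with and without the covariate, and equal to the raw difference in log change (largest difference 0.00000 for both). With offsets varying by ±10% per period, the covariate moved it by at most 0.0035 on the log scale.

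**2. Cost for the interaction.** The SAP gives no between-year correlation r of a home's log rate, so r = 0.4, 0.6 and 0.8 are assumed, with equal variances.

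- SD relative to a baseline-adjusted t2 estimate: √(2/(1+r))
- Correlation with chance baseline imbalance: −√((1−r)/2), against 0 for the adjusted estimate

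| r | SD ratio | Correlation |
|---|---|---|
| 0.4 | √(2/1.4) = 1.20 | −√0.3 = −0.55 |
| 0.6 | √(2/1.6) = 1.12 | −√0.2 = −0.45 |
| 0.8 | √(2/1.8) = 1.05 | −√0.1 = −0.32 |

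A log-rate simulation of 44 homes gave SD increases of 19%, 9% and 4%, and correlations of −0.56, −0.44 and −0.32.

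In the Poisson simulation (assumed rates 0.5 and 1.0 per resident-year) with year-to-year variation, the interaction correlated −0.24 to −0.69 with baseline imbalance. A t2-only model adjusted for the t0 rate gave −0.11 to +0.13. With a year-to-year log-SD of 0.3 and a between-home log-SD of 0.2, the interaction's SD was about 13% to 33% larger. At rate 1.0 and about 100 residents per home that setting has r ≈ 0.04/(0.04 + 0.09 + 0.01) = 0.29, which lies below the range in the table. With little year-to-year variation the SDs were similar.

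**3. Common slope and home variance.** The t0 rows favour a slope of 1 and the later rows a slope of r, so the common slope is about b = (1+2r)/3 = 0.60, 0.73, 0.87. This holds for a log-transformed covariate.

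In the Poisson simulation, adding the covariate cut the estimated home random-intercept SD from about 0.29 to 0.07–0.08 without year-to-year variation, and from about 0.25–0.32 to 0.14–0.17 with it.

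**4. Cost for the t2 group contrast.** Here the covariate does act, with slope b in place of r.

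- SD ratio: √[(1 − 2br + b²)/(1 − r²)]
- Correlation with imbalance: (r − b)/√(1 − 2br + b²)

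| r | b | SD ratio | Correlation |
|---|---|---|---|
| 0.4 | 0.60 | √(0.880/0.840) = 1.024 | −0.21 |
| 0.6 | 0.73 | √(0.658/0.640) = 1.014 | −0.16 |
| 0.8 | 0.87 | √(0.364/0.360) = 1.006 | −0.11 |

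**5. Where a pandemic shock goes.** With a simulated intervention effect of −0.2, a shock of −0.2 common to both arms at t1 and t2 moved the t2 time effect from 0.02 to −0.17. The interaction hardly changed (−0.226 without the shock, −0.234 with it). The common shock is therefore in the time main effect, alongside every other change over time. Only a shock that differs between arms would enter the interaction, where it cannot be told from the intervention effect.

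**The case against.** The strongest reply is that little damage is done. An ordinary group-by-time model is unbiased under randomisation. The covariate does not harm the interaction, because it scarcely touches it. Removing the covariate alone would leave that term as it is, so preferring a constrained-baseline model is largely a matter of efficiency. Section 5.4.2 does not say which contrast will be reported, and the t2 group contrast, the one comparable with the primary result, loses only about 1% to 2% in SD. The penalties depend on a correlation that the SAP does not give and are small when it is high. All this stands, and it limits the size of the point. It does not remove the misstatement: the model lists a baseline adjustment that its group-by-time term does not receive.

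It also stands that section 5.4.2 is not the only place that deals with pandemic disruption. Section 3.2 counts data collection missed because of Covid-19 as a major deviation, and section 5.2 plans per-protocol and adjusted analyses. None of these estimates a Covid-19 effect.

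Three stronger readings are tempting and not supported:

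- **That the double use of t0 is why Covid-19 cannot be isolated.** The reason is the missing Covid-19 variable. Repairing the baseline term would not cure it.
- **That the interaction mixes the pandemic with the intervention.** For a common shock it does not. Arms are randomised within centre and region, and section 2.7 says: "The start of the observation phase (t1) is fixed for all study centres at 01.09.2021". Such a shock cancels between arms.
- **That the model is likely to contradict the primary result.** For the t2 group contrast the figures give this little support.

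**Conclusion.** The point holds, for a supplementary analysis only. As written, the group-by-time term in section 5.4.2 is an unadjusted change score. Its SD is roughly 4% to 20% larger than that of a baseline-adjusted estimate for assumed correlations of 0.8 to 0.4, and it has a clear negative correlation with chance imbalance at t0. The cancellation is exact for offsets constant within a home and near exact otherwise. The common slope is distorted and the home variance understated, while the t2 group contrast is only slightly over-corrected.

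Independently, the stated aim goes beyond the model, which can describe how rates moved in each arm but cannot say how much of the movement was due to Covid-19.

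A reader might infer that the interaction is biased or that the trial's main conclusion is at risk. Neither follows: under randomisation the change score is unbiased on average, and the primary model in section 5.1.2 uses baseline as a covariate only.

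**What to change.** Use t0 once, in one of two ways.

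- **As a response.** Keep t0, t1 and t2 as responses, drop the baseline-rate covariate, and constrain both arms to a common t0 mean, with group effects at t1 and t2 only. This keeps the course from t0 in view. The constraint is the active part. The adjustment then follows the correlation that the fitted variances imply, so a home-by-period random effect should be added if homes vary from year to year beyond Poisson. For example, take a between-home log-SD of 0.3, a year-to-year log-SD of 0.2, rate 1.0 and 100 residents. The true correlation is 0.09/(0.09 + 0.04 + 0.01) = 0.64. A model with a home intercept alone (fitted SD about 0.30) implies 0.09/(0.09 + 0.01) = 0.90 and would over-correct.
- **As a covariate.** Keep the baseline rate, preferably log-transformed, and model only t1 and t2. The slope is then estimated from later periods alone.

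Name the contrast to be reported. Restate the aim as describing hospitalization rates by arm over time, with no claim to estimate a Covid-19 effect. Apply the same wording wherever section 5.4.3 extends this analysis.

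The cost is about two sentences in the SAP, or three with the extra random effect. No new data are needed, and the primary analysis does not change.

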## 2 Study Methods

## 2.1 Trial design

BEVOR is a two-arm, parallel group, prospective, multicenter, cluster randomized controlled trial (cRCT). Nursing homes and related health care providers form the clusters and they themselves (DC1) or, respectively, their residents (DC2) the observation units. The allocation ratio of the clusters is 1:1 for the two groups:

- ACP program (experimental treatment group):
   Each nursing home and related care providers will receive an institutional and regional implementation of the complex German ACP program including a ACP facilitator .
- Care as usual (control group): For each nursing home and health care provider all common care options within the German health care system are available. The control group will receive a delayed ACP intervention after final data collection.

The trial is observer blinded (outcome assessors (until finalization of the SAP) and data collectors are blinded).

44 nursing homes with an average of 96 residents each, from the 4 study centres in Düsseldorf (2 regions), Munich (2 regions), Halle (2 regions) and Göttingen (2 regions) are participating.

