## 3 Statistical Principles

### 3.1 Confidence intervals and P values

All applicable statistical tests will be two-sided and at a 5% significance level. Analyses of secondary outcomes will be performed without adjustment for multiplicity. All confidence intervals presented will be 95% and two-sided.

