### 5.2 Sensitivity analyses

For the primary endpoint analysis, an evaluation with the negative binomial distribution to detect a possible but not expected overdispersion will be performed.

Further, for both primary and key secondary endpoints, per protocol analyses as well as adherence analyses based on NH and resident level will be performed.

Finally, an adjusted analysis is performed taking into account remarkable (p < 0.05) differences at baseline and t1, regarding the following potential confounders:

20

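### The Covid-19 model in SAP 5.4.2 has no term for home-by-year variation, so its time and group-by-time intervals are too narrow whenever homes' rates vary between years beyond Poisson chance

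*SAP*

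**What the plan says.** SAP 5.4.2 plans a mixed Poisson model to look at the pandemic's effect on the primary outcome. Its fixed effects are group, "time (t0, t1, t2) as well as the interaction between group and time as fixed effect, realized follow-up time as offset". The remaining terms are "the respective baseline hospitalization rate as covariate, and region of NHs and the respective NH as random intercept".

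SAP 2.7 fixes the data behind it: "All outcomes on NH level will be measured at t0, t1 and t2 for the preceding 12 months". Each home therefore contributes three yearly counts.

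The only provision for extra-Poisson variation is in SAP 5.2: "For the primary endpoint analysis, an evaluation with the negative binomial distribution to detect a possible but not expected overdispersion will be performed". Section 5.4.2 mentions no dispersion parameter, no NH-by-time effect and no robust variance, and 5.4.3 does not extend the check in 5.2 to this model.

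**The concern.** An NH random intercept suggests that clustering by home has been dealt with. For a comparison between homes at one time point it would largely do that. The time and group-by-time terms, however, compare a home with itself across years. The NH intercept, the region intercept and the baseline-rate covariate all take the same value at a home's three time points, so they essentially drop out of that comparison. What remains is Poisson counting error.

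The model thus assumes that every home's underlying rate moves between years by exactly the shift common to its arm. That is hard to defend in an analysis of a pandemic, where outbreaks would reach different homes in different years. Repeat admissions of the same resident add further variance. If the assumption fails, 5.4.2 will report changes in the arm difference, and changes over time, with more confidence than the data carry.

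**Working it through.** The SAP states no standard error, power or error rate for this model, so there is no figure to reproduce. The check asks what the model's standard error leaves out.

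**Inputs from the SAP**
- "44 nursing homes with an average of 96 residents each" (2.1).
- "The allocation ratio of the clusters is 1:1 for the two groups" (2.1), hence 22 homes per arm.
- "All applicable statistical tests will be two-sided and at a 5% significance level" (3.1).
- Three counts per home (2.7).

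**Assumed, because the SAP gives no value**
- 0.5 to 1.0 hospitalizations per resident-year, so the mean count per home-year is mu = 96 x 0.5 = 48 to 96 x 1.0 = 96.
- Home-by-year SD of the log rate, s, from 0 to 0.20.
- Homes of equal size and no true group-by-time effect.

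**Formulas for the t2-versus-t0 interaction**
- The change in one home's log rate has variance of about 2/mu + 2s². Averaging over 22 homes and differencing two arms gives a true variance of (4/22)(1/mu + s²).
- The model's variance is (4/22)(1/mu).
- The ratio is VIF = 1 + mu·s². The actual size of the nominal 5% test is 2[1 − Φ(1.96/√VIF)].

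| mu | s | VIF | 1.96/√VIF | Actual size |
|---|---|---|---|---|
| any | 0 | 1.00 | 1.96 | 5% |
| 48 | 0.10 | 1.48 | 1.61 | 10.7% |
| 72 | 0.10 | 1.72 | 1.49 | 13.5% |
| 96 | 0.10 | 1.96 | 1.40 | 16.2% |
| 48 | 0.20 | 2.92 | 1.15 | 25.1% |
| 72 | 0.20 | 3.88 | 1.00 | 32.0% |
| 96 | 0.20 | 4.84 | 0.89 | 37.3% |

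At mu = 72 and s = 0.20 the model's SE is √[(4/22)/72] = 0.050, while the true SD is √[(4/22)(1/72 + 0.04)] = 0.099. The intervals are then about half the proper width. The control arm's time effect has half of each variance, hence the same VIF and the same shortfall.

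The joint 2-df group-by-time test has size exp[−5.99/(2·VIF)]. At mu = 72 this is 17.5% at s = 0.10 and 46.2% at s = 0.20.

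**Simulation check.** A Poisson model with an NH random intercept and the baseline-rate covariate (region term omitted) was simulated with 250 runs per setting. The settings were 60 hospitalizations per 100 residents per year, a between-home SD of 0.3 and a home-size SD of 30.
- The t2-versus-t0 interaction was falsely significant in 6.0% of runs at s = 0, 13.6% at 0.10 and 31.6% at 0.20.
- At s = 0.20 the mean model SE was 0.055 against an empirical SD of 0.106.
- Dropping the baseline covariate at s = 0.20 left the single-contrast rate at 31.6%.
- The closed form at this rate (mu = 57.6) gives 11.8% and 28.1% at s = 0.10 and 0.20. The simulated homes differ in size and level, which the closed form ignores.

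**The case against.** **The narrowness is conditional.** SAP 5.2 does not expect overdispersion, and nothing in the document gives a home-by-year variance. With s = 0 the planned model is correctly sized. This stands. A reader might infer that the intervals are certainly too narrow, but the document supports only that they are so whenever such variation is present. Even s = 0.10 doubles or triples the nominal error rate under the assumed counts.

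**The interaction is not a pure pandemic signal.** Under SAP 2.7, t0 is baseline, the run-in lasts from randomization to t1, and the intervention continues to t2. The t2-versus-t0 interaction is therefore also a difference-in-differences estimate of the ACP effect, and a working intervention would make it non-zero. This stands too. A reader might infer that the fault would produce a false claim that the pandemic confounded the primary result. Section 5.4.2 does not say the term will be read that way, and correcting the standard errors would not separate the two effects.

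**It is an additional analysis.** The primary hypothesis is tested by the separate model in 5.1.2, so this point does not put the primary result in doubt. Section 5.4.2 also names no p-value or interval for the interaction, whereas 5.4.1 does for subgroups. The general rule in 3.1 nevertheless supplies two-sided 5% tests and 95% intervals for whatever is reported.

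**The negative binomial check might be thought to cover 5.4.2, because the outcome is the primary one.** Section 5.2 attaches it to the primary endpoint analysis. Section 5.4.2 sets out a different, repeated-measures model without it.

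**The remedies are unevenly tested.** Neither the NH-by-time random effect nor the negative binomial mixed model was simulated. NH-clustered robust errors were tried with a fixed NH effect and gave about 5-7%. A home-level t-test on log-rate changes, with 5,000 runs per setting, held 4.6-5.4%.

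**Conclusion.** The point holds as a conditional variance fault in an additional analysis. That the NH intercept does not protect the time and group-by-time contrasts follows from the model as written. How much this matters depends on a home-by-year variance that the SAP does not give. Under the assumed 48 to 96 hospitalizations per home-year, the single-contrast error rate runs from the nominal 5% at s = 0 to 37% at s = 0.20. Some such variation is plausible in the setting that 5.4.2 is meant to study. The consequence is an overconfident statement that the arm difference, or the rate itself, changed over time. It is worth correcting before the analysis is run.

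**What to change.** Add one sentence to 5.4.2 saying that the estimates, 95% CIs and p-values for time and group-by-time come from a model that allows home-by-period variation. Name one option:

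- an NH-by-time random effect, one per home and time point, added to the NH intercept;
- a negative binomial mixed model for the home-by-time counts; or
- the Poisson model with standard errors clustered by NH and a small-sample correction for 44 homes.

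State as well that the t2-versus-t0 interaction combines the ACP effect with any differential pandemic effect, so that it is not reported as evidence on Covid-19 alone.

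No new data are needed. The cost is wider intervals when home-by-year variation exists. For scale when there is none, the home-level t-test had a mean SE of 0.061 at 60 hospitalizations per 100 residents per year, against 0.056 for the planned model (0.061/0.056 = 1.09). The listed options were not costed separately.
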